2. Determine whether health literacy mediates the relationship between baseline demographics (e.g., education, age, gender) and future stress-related symptoms using the PCL-5. Will run separate models for English and Spanish.
3. Determine which aspects of health-related quality of life (measured by PROMIS-57 Profile v2.1, which includes Physical Function, Anxiety, Depression, Fatigue, Sleep Disturbance, Ability to Participate in Social Roles and Activities, Pain interference, and Pain Intensity) are associated with trauma symptoms measured by the PCL-5, after statistically controlling for demographics and health literacy.

Hypotheses:

1. There will be a significant association between health literacy (measured by Health LiTT) and the PCL-5 scale, such that lower health literacy will be associated with higher trauma-related symptoms.
2. Health literacy serves as a mediator between baseline demographics (education, age, gender, ethnicity) and future stress related symptoms as per the PCL-5.
3. Higher levels of self-reported anxiety, depression, and ability to participate in social roles and activities from the PROMIS-57 will be associated with higher PCL scores.

Data Description

Datasets used

NIH-funded Reducing Assessment Barriers for Patients with Low Health Literacy dataset, also known as the DIF study (PI: [name]). All timepoints will be analyzed for this project (baseline, 3-month, and 6-month time points). The dataset is not publicly available. The data are not public, but will be made available to us from the DIF team at the time of publication.

Data Collection Procedures (from parent study)

Participants included those who were aged 18 or older, could provide informed consent, were open to randomization for mode of administration, were willing to complete questionnaires, fluent in English and/or Spanish, willing to attend three face-to-face sessions, and did not have plans to move outside of the study area for six months. Study participants were recruited from two sites: Northwestern University (Chicago, IL) and Boston Medical Center (Boston, MA). Participants were ineligible for the study if they had significant cognitive

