For Aim 3, we will conduct analysis that aims to identify which aspects of health-related quality of life (as measured by the PROMIS-57 Profile v2.1) are associated with posttraumatic stress-related symptoms (as measured by the PCL-5). The PROMIS-57 includes domains such as Physical Function, Anxiety, Depression, Fatigue, Sleep Disturbance, Ability to Participate in Social Roles and Activities, Pain interference, and Pain Intensity. We will examine the relationship between these quality-of-life domains and trauma symptoms while statistically controlling for demographic variables and health literacy. For this analysis, we will begin with assessing the correlations (using the psych package in R) between the PROMIS-57 domains and PCL-5, in the overall sample and also stratified by language. This may identify any significant relationships between quality of life domains and posttraumatic stress symptoms. Domains that suggest association with posttraumatic stress symptoms will be entered into a regression model with demographics included as covariates (to control for potential influence) and further evaluate the distinctive influence of quality of life domains predicting trauma symptoms. Lastly, language will be used as a moderator in the regression model to assess whether these relationships differ by language.

Effect size

I am focusing on unstandardized regression coefficients. In some cases, I may inspect standardized regression coefficients.

Inference criteria

Any regression coefficients with a 95% CI not containing zero will be regarded as significant.

Assumption Violation/ Model Non-Convergence

We will inspect the distribution of residuals for each model. If residuals suggest a departure from normality, robust regression and/or bootstrapping will be considered. If a model does not converge, we will explore other estimators in lavaan or modifications to the model, such as dropping covariates that are not needed.

Exploratory analysis

For research questions 1 and 3, language will be explored as a moderator. For research question 2, we will explore separate models for English and Spanish.

REFERENCES CITED

1. Affairs HlrotCoS. Ad Hoc Committee on Health Literacy for the Council on Scientific Affairs, American Medical Association. *JAMA*. 1999;281(6):552-7.

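### PCL-5 Aim 3 screens PROMIS domains on an undefined correlation with the outcome before an adjusted regression on the same data, and its text is inconsistent on whether health literacy is a covariate

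*SAP*

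**What the plan says.** The section is the SAP's *Health Literacy as a Possible Mediator Between Demographics and Symptoms Related to Stress and Trauma*, added for Version 5.1.

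- **Aim.** The third aim asks which quality-of-life domains are associated with PCL-5 "after statistically controlling for demographics and health literacy".
- **Hypothesis 3.** It names three of the domains in advance: anxiety, depression, and ability to participate in social roles and activities.
- **Candidates.** The Aim 3 description lists eight domains: "Physical Function, Anxiety, Depression, Fatigue, Sleep Disturbance, Ability to Participate in Social Roles and Activities, Pain interference, and Pain Intensity".
- **Adjustment, as introduced.** The same description says the relationship is examined "while statistically controlling for demographic variables and health literacy".
- **Screen.** The analysis starts with marginal correlations: "we will begin with assessing the correlations (using the psych package in R) between the PROMIS-57 domains and PCL-5", in the whole sample and by language.
- **Regression.** "Domains that suggest association with posttraumatic stress symptoms will be entered into a regression model with demographics included as covariates". Language is then used as a moderator in that regression.
- **Inference.** "Any regression coefficients with a 95% CI not containing zero will be regarded as significant".

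No correlation, p-value or interval width is given for passing the screen. There is no rule for a domain that passes overall but not within a language. Aim 3 has no model code; the example code for Aim 1 does include Health LiTT beside the demographics.

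**The concern.** Aim 3 is about adjusted associations, and the Aim 3 description says the regression should bring out what each domain contributes on its own. A marginal correlation answers a different question. A domain whose own association is masked by its correlation with other domains can have a near-zero marginal correlation and never reach the model that would show it. Nothing exempts the three domains of Hypothesis 3 from the screen, so a stated hypothesis could be removed before its adjusted test.

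The screen and the test also use the same outcome in the same participants. A weak domain tends to be kept when chance has made its association look larger, and an ordinary 95% interval takes no account of that. Because the cut-off is undefined, two analysts following the plan could fit different models.

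The covariate wording adds a second ambiguity. Read alone, the sentence that specifies the regression leaves out a variable that Hypothesis 1 of the same section expects to be related to PCL-5.

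**Working it through.** The documents give no sample size, power or error rate for Aim 3, so there is no figure to reproduce. The check is a comparison of the text, followed by illustrations whose inputs are labelled as assumed.

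**1. Covariate set, place by place**

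| Place in the SAP section | Adjustment set |
|---|---|
| Aims, item 3 | demographics and health literacy |
| Aim 3 description, overview sentence | demographics and health literacy |
| Aim 3 description, regression sentence | demographics only |
| Aim 3 code | none given |

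Two statements include health literacy, one omits it, and none excludes it.

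**2. How a marginal screen can lose a domain**

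Assumed: standardized coefficients 0.5, 0.3, 0, 0, 0, 0, −0.20, −0.25; every pair of domains correlated 0.3; outcome variance 1. The marginal correlation of domain j is βj + 0.3 × (sum of the other coefficients).

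- Seventh domain: −0.20 + 0.3 × (0.5 + 0.3 − 0.25) = −0.20 + 0.165 = −0.035
- Eighth domain: −0.25 + 0.3 × (0.5 + 0.3 − 0.20) = −0.25 + 0.18 = −0.07
- Each null domain: 0.3 × (0.5 + 0.3 − 0.20 − 0.25) = 0.3 × 0.35 = 0.105

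If the screen were p < .05 (assumed) at n = 728, the critical |r| is t/√(t² + 726) with t = 1.963, which is about 0.073. Two real adjusted effects lie below that value, and the null domains lie above it.

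**3. Simulated two-stage procedure against all eight domains in one model**

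Assumed: screen at p < .05; n = 728 (the SAP's count with a health literacy assessment, used as an upper bound) or 300 (an assumed lower value); no other covariates. There were 1,500 runs per setting, and 2,000 where all domains are null. Coverage and flag rates in the two-stage column are for domains that entered the regression; *flagged* means the 95% interval excludes zero.

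| Assumed truth | n | Domains entering | Two-stage result | All-eight model |
|---|---|---|---|---|
| A: 0.4, 0.3, six null; r = 0.5 | 728, 300 | all, in essentially every run | coverage 94–96%; nulls flagged 4–6% | same |
| B: 0.4, 0.3, two at 0.05, four null; r = 0 | 728 | weak 28%; null 4–6% | weak: mean absolute coefficient 0.085, coverage 88–90%; null coverage 39–55% | nulls flagged 4–5% |
| B | 300 | weak 13–14%; null 4–5% | weak: 0.117, coverage 84–86%; null coverage 34–55% | nulls flagged 4–6% |
| C: as in step 2 | 728 | −0.20: 15%; −0.25: 48%; null 81–82% | two strongest: coverage 75% and 77%; nulls flagged 14–16% | both negative effects flagged about 100%; nulls 4–5% |
| C | 300 | 10%; 22%; null 43–46% | two strongest: coverage 75% and 73%; nulls flagged 3–4% | 96% and 100%; nulls 5–6% |
| D: all null; r = 0.5 | 728, 300 | 4–5% each | entered nulls flagged 38–52% | nulls flagged 4–6% |

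**4. If health literacy were left out**

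Standardized bias in a domain coefficient is approximately (health literacy coefficient) × (domain–health literacy correlation given demographics). Assumed ranges: coefficient −0.05 to −0.30, correlation −0.1 to −0.3.

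- Smallest: −0.05 × −0.1 = 0.005
- Largest: −0.30 × −0.3 = 0.09

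**5. Multiplicity once the screen is gone**

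With eight independent null domains at 0.05 each, the chance of at least one false positive is 1 − 0.95⁸ = 0.337. The simulations with all domains null gave 0.31 to 0.34 for the all-eight model.

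**The case against.** **Health literacy.** A reader might infer that the regression is run without health literacy, so that the results are not adjusted as the aim states. The documents do not support that. The promise to control for it appears in the aim and again in the Aim 3 paragraph, before the sentence at issue. What stands is an incomplete covariate list that should be reconciled.

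**Size of the omitted-covariate effect.** One can choose correlations that make it look large. With domain–PCL-5 −.15, domain–literacy .3 and literacy–PCL-5 −.2, the adjusted value is (−.15 + .06)/.91 = −.099, so the unadjusted one is about half as large again. Put −.50 in place of −.15 and the result is (−.50 + .06)/.91 = −.484, a difference of about 3%. All these inputs are invented and demographics are left out, so neither figure describes this study.

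**Spanish speakers.** A reader might also infer that the screen does most harm in a Spanish sample of at most 728 − 566 = 162. That subtracts two differently defined counts: everyone with a health literacy assessment, and English speakers with baseline data through March 2020. Aim 3 plans language-stratified correlations but a single regression with language as moderator. No Spanish-only regression is specified.

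**Harm may be nil.** This stands. In setting A every domain passes and the two procedures coincide. The larger distortions need offsetting or mostly null effects, which the documents neither state nor rule out. Nor does the screen always raise the overall count of false flags. The chance of at least one null domain being flagged, two-stage against all-eight, is 0.090 against 0.165 in B at n = 728, and 0.368 against 0.165 in C at n = 728, but 0.061 against 0.189 in C at n = 300.

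**It is exploratory.** The section sits under *Other Interim and Exploratory Analyses*, away from the primary DIF work, and that limits the weight of the point. But it has its own numbered hypotheses and significance rule, and its own exploratory paragraph covers only the language analyses.

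**Conclusion.** The point holds. Aim 3 uses a marginal screen with no cut-off on the outcome it then tests, with ordinary 95% intervals and no hold-out or correction, to answer a question about adjusted associations. The screen can drop a domain that matters only after adjustment, including those in Hypothesis 3, and can make intervals for weak retained domains anti-conservative.

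The size cannot be fixed from the documents. Under the assumed p < .05 screen it ran from no effect (A), through moderate under-coverage for weak retained domains (B), to real adjusted effects screened out in most runs and about 75% coverage for the strongest domains (C). The correlations among domains, their effects and the sample size were all assumed.

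On health literacy, the finding is an internal inconsistency only. It would matter if an analyst followed the regression sentence literally, with an assumed standardized bias of 0.005 to 0.09 per domain coefficient.

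The change is worth making because a better model is available at little cost. It does not bear on the study's primary analyses.

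**What to change.** Replace the two-step description with one pre-specified linear model for PCL-5 that contains:

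- all eight PROMIS-57 domains, with no bivariate screen;
- continuous Health LiTT;
- each demographic covariate by name. Aim 1 lists education, age, gender, race and ethnicity; because it analyses race and ethnicity in English speakers, state how that applies to a model with both languages.

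Report all eight coefficients with intervals whatever their size. Give the domain–PCL-5 correlations, overall and by language, as description only. Keep language as the moderator. Amend the regression sentence so that it agrees with the aim and the overview sentence on health literacy.

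This does not remove multiplicity. Either acknowledge the roughly 0.34 chance of at least one false positive, or label results beyond the three domains of Hypothesis 3 as exploratory.

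If a screen is kept, state its cut-off, say how overall and language-specific results combine, exempt the Hypothesis 3 domains, and validate the procedure by bootstrap or on held-out data.

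The cost is SAP wording, a few more model terms and slightly wider intervals because the domains are correlated. No new data are needed.
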